1.2 Intended use of the investigational device

In the proposed study, the efficacy of using NeuroPort Arrays (K070272) for chronic (>30 days) recording of neural signals in humans will be investigated. No modifications are being made to the Arrays as part of this investigation.

We will implant 2 NeuroPort Arrays in the motor cortex of individuals with limited or no ability to use both hands due to cervical spinal cord injury or brainstem or spinal stroke. The NeuroPort Arrays will be implanted for 1 year (+/- 30 days). Study participants will learn to control their neural signals (brain electrical activity) recorded from the NeuroPort Arrays in order to control a variety of external devices including virtual reality objects, a motorized prosthetic limb and a robotic arm exoskeleton in a safe environment. Demonstration of successful control of these devices will support our hypothesis that implantation of two NeuroPort Arrays allows for recording of sufficient neural information to control a complex BMI that can augment impaired motor functions.

For the proposed extension study, we are requesting a supplement to this IDE to allow for implantation duration of up to 5 years. This extension study will allow us to quantify BMI performance and signal quality over a longer duration.

The 510(k) approval for the NeuroPort Arrays describes the indications for use as:

“The intended use of the Cyberkinetics Neurotechnology Systems, Inc. NeuroPort Microelectrode Array System is for temporary (<30 days) recording and monitoring of brain electrical activity”. This 510(k) was purchased by Blackrock Microsystems from Cyberkinetics Neurotechnology Systems, Inc.

For the proposed investigation, the investigational indication for use would be:

“For chronic (>30 days) recording and monitoring of electrical activity from the motor cortex, in individuals with cervical spinal cord injury or stroke, to control external devices such as computers, assistive devices, and potentially robotic devices”.

The neural signals will be processed and recorded by the NeuroPort System as indicated by the current 510(k) approval (K090957). The NeuroPort System includes a patient cable which connects to the percutaneous pedestal connector of the NeuroPort Array, a neural signal processor, a front end amplifier/digitizer, and a computer and display monitor. The indications for use of the NeuroPort System are:

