1.3 Objectives of the clinical investigation

The proposed clinical investigation is a feasibility study directed toward:

Specific Aim 1: Investigate the safety and efficacy of using NeuroPort Arrays for chronic recording of neural activity from the motor cortex of individuals with upper limb impairments.

- Specific Aim 1a: Document the safety of using the NeuroPort Arrays for chronic recording of neural activity. Monthly neurological and physical examinations will be conducted and documented for the duration of the trial. Any serious adverse events that occur as part of this investigation will be reported in accordance with the FDA’s expedited reporting requirements.
- Specific Aim 1b: Characterize signal quality recorded with the NeuroPort Array during long term implantation in the motor cortex of individuals with tetraplegia. Primary measurements of signal quality include the number of units recorded by the array and the firing rate of single neurons measured during specific tasks (such as imagined hand movement) [6, 45, 46].

Specific Aim 2: Demonstrate that individuals with tetraplegia can learn to successfully control a variety of external devices and computer-driven tasks using signals recorded with two NeuroPort Arrays. We aim to achieve high-dimensional control of complex systems including both a virtual and robotic dexterous hand and arm to perform grasping and reaching tasks which are essential for activities of daily living. This will be measured over the duration of implantation by computing success rate for a given task as well as the amount of computer assist that is required.

Specific Aim 3: Use MEG to localize areas of the brain that can be voluntarily modulated. These results will be compared to pre-surgical mapping results with fMRI and provide additional information for planning the location of electrode implantation.

- Specific Aim 3a: At the optional follow-up MEG visits, we will use the same paradigms to localize areas of the cortex that can be voluntarily modulated to determine if BMI training has induced neuroplasticity. We expect the areas of cortex responsible for voluntary movement will be more strongly activated with more localized responses.

Specific Aim 4: Conduct a sleep study to measure the quantity and quality of sleep each night for a specified period of time to help clarify the role of sleep in motor learning.

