At the beginning of each BMI testing session, an investigator will connect the Patient Cable to the Patient Pedestal. There are two types of behavioral tasks that the subjects will participate in as part of the BMI Training/Testing:

1. Open-loop tasks:

In the so-called "open-loop" tasks, subjects respond (with movement or other action) to a simple stimulus (such as visual or audio cue). Kinematics and muscle activity may be recorded using a DataGlove (a wearable glove that measures the finger joint movement), EMG electrodes, or motion tracking system. These tasks are used to identify associations between the user's action and neural activity in the brain. The type of data that will be recorded will be dependent on the participant's injury level and completeness. Some participants may not have any residual motor or sensory function in the upper limb and may not perform these tasks. In some cases the kinematic or EMG data will be used to verify that no overt movement is occurring.

Examples of sensory inputs include:

- Visual cue (e.g. prompt on a computer screen)
- Audio cue (e.g. tone or spoken word)
- Somatosensory
 - Passive movement of a limb
 - Peripheral nerve stimulation: Here a small metal disc electrode is placed on the arm or leg to deliver an electrical stimulus which results in an evoked-potential in the brain. The stimulus level will be adjusted so that the subject is able to feel the stimulation, but is not uncomfortable.
 - Vibrotactile feedback

Examples of user responses include:

- Real, imagined, or observed movement (e.g. opening and closing the hand, tapping fingers, or protruding the tongue)
- Cognitive response (e.g. describing an object or saying a word)
- Interaction with a human interface device (e.g. mouse, joystick, or DataGlove)

2. Closed-loop tasks

In the so-called "closed-loop" tasks, the computer cursor (or other output signal) is controlled by neural signals recorded and processed by the BMI system. The subject is trained to willfully modulate their neural signals to achieve the desired output. We have the capability to provide "computer-assist" which blends the neural signals with an optimal control signal in order to ensure some level of successful completion. This will facilitate learning and keep the participant motivated. The assist level will be documented and the goal is to reduce the assist level to 0% so that the participant has full neural control over the output signal.

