2.5.3 Outcome data and data analysis

Specific Aim 1a will be fulfilled through monthly clinical examinations as well as observations made by the research staff, participant, or their caregiver throughout the trial. Research staff will document volunteered and observed adverse events at least weekly during the BMI training sessions. Adverse events will be documented and reported to University of Pittsburgh IRB and to the FDA in accordance with the respective reporting requirements and in the annual report. This documentation will serve as documentation of the safety of device in this small sample.

Specific Aim 1b is to characterize signal quality (firing rate, number of units recorded) over the duration of implantation. Data to support this aim will be collected at least weekly during the BMI training sessions. Our primary method of analysis will be to plot the trends in signal quality measures over time. The trend will be quantified using regression techniques.

Specific Aim 2 is to demonstrate that individuals with tetraplegia can learn to successfully control of a variety of external devices and computer-driven tasks using signals recorded with the NeuroPort Array. In addition to video documentation of brain-controlled device operation, we will quantify the number of degrees of freedom achieved by each participant at regular intervals for the duration of implantation. Multiple baselines will be defined as the level of computer assist will decrease with training. We will use regression to quantify changes in performance at a given assist level. Similarly, trends in success rate and computer assist level for a given task will be quantified over the duration of the trial using regression.

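### Aim 2 reports raw success rates with no no-information reference, so success levels under computer assist or in simple tasks, and trends across changing task settings, cannot be attributed to neural control

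*Combined protocol and SAP*

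**What the plan says.** Section 1.2 states the inference: "Demonstration of successful control of these devices will support our hypothesis that implantation of two NeuroPort Arrays allows for recording of sufficient neural information". Section 1.3 measures Aim 2 by "computing success rate for a given task as well as the amount of computer assist that is required".

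Section 2.4.2 (closed-loop tasks) describes assist as a facility "which blends the neural signals with an optimal control signal in order to ensure some level of successful completion". The level is documented, and "the goal is to reduce the assist level to 0" per cent.

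The analysis is in section 2.5.3, repeated in 3.5.3 for the extension. Besides video and the number of degrees of freedom achieved, it has three parts:
- "Multiple baselines will be defined as the level of computer assist will decrease with training".
- Within any one assist level, a regression describes how performance changes.
- "trends in success rate and computer assist level for a given task will be quantified over the duration of the trial using regression".

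The baselines are tied to assist levels, not to a condition without neural input. Neither the core nor the extension protocol contains a chance level, an assist-only run, a sham or shuffled signal, or any other no-information rate. Section 10.1 says that target size, target location and assist level are saved with the data, but plans no such use of them.

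**The concern.** A success rate supports a claim about neural information only by the amount it exceeds what the same task would yield without that information. Under assist, successes come partly from the optimal signal. In a simple task, some come from undirected movement. The plan reports the mixture and never separates the parts.

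This affects two kinds of statement. The first is any statement about the level of success at non-zero assist or in a low-dimensional task. The second is any trend during which the configuration changes. The documents expect such changes: section 4.1 (BMI training risks) says that tasks may have to be made easier and less complex as signals degrade in the extension. Section 1.3 hopes to learn whether plasticity or new training can offset that degradation. An easier task raises the no-information rate just as the signal falls, so a flat raw success rate could be read as compensation. For Aim 4, section 3.5.3 controls for task difficulty; Aim 2 has no such provision.

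**Working it through.** The plan has no figure to reproduce. It gives no chance rate, target geometry, time limit, cursor speed or number of trials for Aim 2. Everything numerical below rests on assumptions and is illustrative.

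**1. Fixed task and fixed assist.** Let p0 be the no-information success rate, O(t) the observed rate and G(t) = O(t) − p0 the gain. If p0 is constant, the slope of O equals the slope of G. The planned regression within an assist level is therefore protected, provided that the configuration behind the task name stays the same.

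**2. Size of p0.** A cursor is simulated with velocity = (1 − a) × noise + a × optimal signal, where a is the assist fraction and the noise carries no information. Assumptions: target at distance 1, target radius 0.1 to 0.3, speed 0.03 per step, 100 steps, noise autocorrelation 0.9 per step, no hold time, 4,000 trials per cell. No-information success over the range of radii:

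| Dimensions | a = 0% | 30% | 40% | 50% |
|---|---|---|---|---|
| 1 | 33-40% | 54-67% | 69-78% | 85-91% |
| 2 | 4-13% | 28-49% | 52-74% | 82-94% |
| 3 | 0.5-4% | 14-38% | 40-70% | 81-95% |

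**3. Sensitivity.** A second version used 10 s trials, radius 0.15 or 0.25, hold 0 or 0.5 s, noise time constant 0.5 s and noise speed equal to assist speed. For two dimensions at 40% assist:
- 0.2 start distances per second: 27-51%
- 0.3 per second: 67-80%
- 0.5 per second: 86-93%

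Moderate variation of speed and noise together gave about 25-93%. With speed 0.3 to 1.0 and noise 0.5 to 4 times assist speed, the range was 1% to 100%.

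**4. A change of configuration.** In the first simulation, two dimensions at 40% assist, enlarging the radius from 0.1 to 0.3 moves p0 from 51.8% to 73.6%: 73.6 − 51.8 = 21.8 percentage points with no neural contribution. At 0% assist the same change gives 13.1 − 4.2 = 8.9 points.

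**5. What an observed rate would have to reach.** Smallest number of successes with an exact binomial upper tail of at most 0.05 (an assumed one-sided level):

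| p0 | 20 trials | 80 trials |
|---|---|---|
| 0.05 | 4 | 8 |
| 0.125 | 6 | 16 |
| 0.25 | 9 | 27 |
| 0.50 | 15 | 48 |
| 0.80 | 20 | 71 |

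The required rate runs from 8/80 = 10% to 20/20 = 100%, depending on a reference that the plan does not define.

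**The case against.** The other side has a good deal in its favour.
- The plan regresses performance within an assist level and for a given task, where step 1 shows the slope is safe.
- Assist is recorded and is itself a trended outcome, so raising it cannot pass unnoticed as learning. A participant contributing nothing should show no sustained fall in assist.
- Analyses are single-subject (section 2.5.2), and no comparison of success rates between participants is planned.
- The efficacy criterion in section 2.5.3 is control of a device with many degrees of freedom, and extension entry (section 3.3.3) asks for at least four-dimensional control. Unassisted no-information success was already only about 0-5% in three dimensions.
- Aim 1b tracks units and firing rates separately.
- This is a feasibility study with at most five implants and no hypothesis test for Aim 2.

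All of this stands, and it limits the point. It does not remove it. Zero assist is a goal in section 2.4.2, not a condition of the analysis or of the success statement in section 2.5.3. The planned reports include success levels at non-zero assist. Nothing keeps target size, time limit or complexity constant under one task name.

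A reader might go further and infer that the Aim 2 trends are invalid throughout, or that a participant with no usable signal would be declared a success. The documents support neither, for the reasons above. Nor do they support quoting a particular assisted percentage as pure chance: the inputs are absent and the range is too wide. The only numerical success threshold, about 75% in section 4.1, is a safety precaution before close contact with the robotic arm, not an Aim 2 criterion.

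**Conclusion.** The point holds in a limited form. The planned analysis does not support statements about the absolute level of control at non-zero assist or in low-dimensional tasks. It also does not support trends that cross changes in target size, time limit, complexity or assist. Trends at a fixed configuration and assist level, and unassisted high-dimensional demonstrations, are largely unaffected.

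The omission, and the fact that assist generates successes, come from the documents' own text. That simple unassisted tasks have a material chance rate is an inference, and its size rests on assumed geometry, speed and noise. The simulations show that the no-information rate varies widely with settings; they do not estimate its value in this study. The analysis should be changed, but the gap does not undermine the feasibility design.

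**What to change.** In sections 2.5.3 and 3.5.3:

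1. For each task configuration and assist level entering the regressions, report a no-information success rate beside the raw rate. Obtain it from an assist-only run or a simulated noise-input run with the saved target and assist settings. Name the method in advance, since the two can differ. At 0% assist only the noise-input run is informative, because assist alone produces no movement.
2. Log time limit, hold requirement and decoder settings as well. Section 10.1 does not list them among its examples of saved parameters.
3. Report observed minus no-information success with an interval.
4. Hold task configuration fixed within each regression, or include it as a covariate.
5. Base statements of successful control on 0% assist trials, or on assisted trials only where success clearly exceeds the no-information rate.

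Two shortcuts should be avoided. Replaying recorded closed-loop signals against permuted targets should not be the sole reference: those signals are purposeful commands toward another target, so they are not free of information. Exceeding the no-information rate should not by itself count a degree of freedom as achieved: with p0 = 0.05 and 80 trials, 10% success would pass, and a task-level rate does not give a chance rate for each degree of freedom.

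The cost is modest offline work and a few more logged settings. Simulated references need no participant time. Assisted performance will look smaller.

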(1) Neuropsychological examination: Participants will complete a neuropsychological assessment with a trained psychologist. We will use the Wechsler Test of Adult Reading (WTAR) and Brief Symptom Inventory (BSI-18) to assess intellectual functioning and psychological distress. If the subject does not have a normal result on the neuropsychological examination, they will be excluded. The WTAR measures intellectual functioning and the BSI-18 measures mental

health. Psychosocial health and support will also be assessed by interview with the psychologist. This examination is expected to take less than 30 minutes and will be performed in University of Pittsburgh or UPMC research space.

(2) Pre-surgical screening to localize cortical activity during imagined or attempted movement: fMRI will be used as the gold standard to localize the cortical area where the NeuroPort Arrays will be implanted. fMRI testing will be completed at the Magnetic Resonance Research Center at UPMC Presbyterian Hospital. Subjects will be asked to complete simple tasks during the fMRI scan. For example, subjects may be asked to view, imagine, or attempt hand and upper limb movements, speaking, or tongue movements. The goal of the fMRI scan is to create a map of motor cortical areas in order to guide the surgical procedure. The fMRI is expected to take less than 1 hour.

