2.5.2 Sample size determination

A maximum of 10 participants will be enrolled in order to implant a maximum of 5

subjects. Because it is possible that a subject may enroll and then be determined to be ineligible for anesthesia and/or surgery, the maximum number of subjects enrolled may exceed the number implanted.

New information will be learned with each participant, as this is a feasibility study. Single-subject design statistical analyses will be used. Our main goal is to demonstrate the safety and efficacy of NeuroPort Arrays for long-term recording of neural activity in order to control a high-dimensional BMI.

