Specific Aim 3: Source localization (combining the MEG and structural MRI data) will be used to identify the anatomical foci of cortical activation controlling imagined and/or attempted movement. The coordinates (x,y,z) of the center of activation can be computed with fMRI or MEG relative to the head coordinate system defined using bony landmarks. The location and area of cortical activation measured by fMRI and MEG during imagined and/or attempted movement will be compared for each subject. A paired t-test will be used to compare location and area of cortical activation measured by the two imaging techniques using data from all participants, although the power of this test may be limited by sample size. Qualitative comparisons will be informative and we expect agreement between the two imaging techniques in terms of localizing the area for array implantation. MEG

potentially offers additional information due to higher temporal resolution.

Specific Aim 3a: Cortical modulation will be calculated as the power of the 4-40 Hz frequency band of MEG data that is recorded during imagined and/or attempted movement. Specific Aim 3a will be evaluated by applying repeated measures ANOVA to test for differences in modulation (magnitude and total area) during imagined and/or attempted movement during the pre-surgical procedures and the follow-up sessions.

The study will be considered a success if the device is not explanted for safety reasons during the 12-month post-implant evaluation. Further participants should demonstrate successful control of a high degree of freedom assistive technology in order to safely perform a task that replicates normal activities of daily living, such as grasping a cup with a robotic manipulator. This study is not being proposed to support marketing applications (510(k) or PMA) for the NeuroPort Arrays. Instead, the goal is to demonstrate that three-dimensional microelectrode arrays provide a safe way to record sufficient neural information for controlling complex assistive devices that will increase the independence of individuals with disabilities.

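### Aim 3 expects fMRI and MEG to agree on location, but the only statistic it names detects mean shift; lead with each participant's distance and area difference

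*Combined protocol and SAP*

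**What the plan says.** Section 2.5.3, under Specific Aim 3, describes the fMRI-MEG comparison in several steps.

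- It defines the measures: area, and coordinates (x, y, z) "of the center of activation can be computed with fMRI or MEG relative to the head coordinate system".
- It plans an individual comparison: "The location and area of cortical activation measured by fMRI and MEG during imagined and/or attempted movement will be compared for each subject".
- It names one statistical method, pooled over all participants: "A paired t-test will be used to compare location and area of cortical activation measured by the two imaging techniques". The caveat attached is "although the power of this test may be limited by sample size".
- It then adds: "Qualitative comparisons will be informative and we expect agreement between the two imaging techniques in terms of localizing the area for array implantation".

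Section 3.5.3 repeats this text for the extension study. Section 2.5.2 sets the general approach: "Single-subject design statistical analyses will be used". Sections 2.3.2 and 2.5.2 cap enrolment at 10 and implantation at 5.

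Neither section defines a distance between the two centres, limits of agreement or a margin. Neither says how location enters the t-test, for example one axis at a time.

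**The concern.** Whether two techniques agree on a location is a question about each participant: how far apart are the two centres? A paired t-test answers a different question, namely whether the average signed difference over participants departs from zero. If MEG lies well in front of the fMRI centre in some participants and well behind it in others, the average can be near zero while the techniques disagree in everyone.

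At stake is how well Aim 3 can describe agreement. The individual comparison is intended, but no measure is attached to it. The only named statistic would therefore leave scatter between the techniques unreported, apart from a qualitative account.

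**Working it through.** **Inputs.** The plan gives no significance level, standard deviation, expected difference or margin for Aim 3, so there is no figure of its own to reproduce. I assume a two-sided 5% level and normally distributed differences. All millimetre values below are assumptions for illustration. The sample sizes 5 and 10 are the plan's caps on implantation and enrolment. The n = 3 case allows for participants without MEG, whom section 2.4.2 keeps in the study.

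**Step 1: what the test sees.** A paired t-test needs one value per technique per participant. The plan supplies x, y, z and area. For any one of these, with d = MEG minus fMRI,

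t = mean(d) / (SD(d) / √n).

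Only the mean of the signed differences is in the numerator. Multiplying every difference by a constant leaves t unchanged. So when the true mean shift is zero, the rejection rate is 5% per axis whatever the scatter and whatever n. Simulation at SD 3, 5 and 10 mm and n = 3, 5 and 10 gave 4.9% to 5.0%.

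**Step 2: what the scatter does meanwhile.** With independent axes, zero mean and equal SD, the mean 3-D separation is SD × √(8/π) = 1.596 × SD. The expected largest of five separations is 2.421 × SD.

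| SD per axis (assumed) | Mean separation | Expected largest of 5 | Rejection per axis |
|---|---|---|---|
| 3 mm | 4.8 mm | 7.3 mm | 5% |
| 5 mm | 8.0 mm | 12.1 mm | 5% |
| 10 mm | 16.0 mm | 24.2 mm | 5% |

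Separation more than triples down the table, and the test does not respond.

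**Step 3: two illustrative sets, one axis, n = 5.**

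- Differences -12, -8, +2, +8, +12 mm: mean 2/5 = 0.4, SD 10.24, t = 0.4 / (10.24/√5) = 0.087, p = 0.935, 95% CI -12.3 to 13.1. Mean absolute difference 42/5 = 8.4 mm, largest 12 mm.
- Differences +1, +2, +3, +1, +3 mm: mean 2.0, SD 1.0, t = 2.0 / (1.0/√5) = 4.47, p = 0.011, 95% CI 0.76 to 3.24. Mean absolute difference 2.0 mm, largest 3 mm.

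The second set is the closer one, and it is the one with the significant result. The sets were chosen to make the mechanism visible; they do not predict the trial's data.

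**Step 4: does the power caveat cover this?** It covers detection of a mean shift. The shift needed for 80% power is 1.68 SD at n = 5 and 1.0 SD at n = 10, so more participants help there. By step 1, they do nothing for scatter around zero.

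**Step 5: precision of a mean signed difference.** The 95% half-width is t(0.975, n-1) × SD / √n: 2.48 SD at n = 3, 1.24 SD at n = 5 and 0.72 SD at n = 10. The last is a ceiling, since Table 1 (2.4.5) places MEG after screening and MEG can be skipped.

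**The case against.** The strongest reply is that the plan does not use the t-test to establish agreement. The expectation of agreement sits in the sentence on qualitative comparison. The individual comparison is already planned, and a distance follows directly from the coordinates named. On that view the only gap is an unnamed summary measure. Much of this stands. A reader might infer that the investigators would report agreement from a non-significant result, and so could rank the techniques' agreement the wrong way round. No section says that a non-significant result will be read so, and the reversal in step 3 does harm only if someone draws that inference.

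It is also fair that the plan leaves open how location enters the test. The argument here assumes the coordinate form, the only form section 2.5.3 defines. Any other single signed value per technique would behave in the same way. A mean shift is a legitimate part of the comparison, and for area a mean difference is an ordinary first analysis.

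Finally, little rests on this test. Section 2.4.1 says: "fMRI will be used as the gold standard to localize the cortical area where the NeuroPort Arrays will be implanted". Section 2.4.2 keeps participants without MEG in the study and allows intraoperative mapping in some. Success is defined elsewhere in 2.5.3: "The study will be considered a success if the device is not explanted for safety reasons during the 12-month post-implant evaluation", together with control of an assistive device.

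What remains is that the one named statistic does not measure the agreement the aim expects, and the power caveat does not repair that.

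**Conclusion.** The point holds, and it is minor. On the coordinates defined in 2.5.3, the only quantitative fMRI-MEG method named assesses systematic mean shift. Under zero shift it rejects at 5% per axis however far apart the two centres lie, at any sample size. This follows from the form of the t statistic and does not depend on the illustrative millimetre values; it assumes normal differences and a test on signed coordinates.

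The consequence is confined to how well Aim 3 can describe agreement. A reader might go further and infer a threat to array placement or to the study's success criterion. The documents do not support that: fMRI is the localization reference, and success does not use this test.

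**What to change.** In section 2.5.3, with a conforming edit in 3.5.3:

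1. Make two quantities the leading Aim 3 comparison for each participant: the Euclidean distance between the fMRI and MEG centres, √(Δx² + Δy² + Δz²), and the difference in area. List them individually, with mean and maximum. This supplies the measure missing from the planned per-subject comparison and fits the single-subject approach of 2.5.2.
2. Keep the paired analysis as a check for systematic shift only. Report the mean signed difference (MEG minus fMRI) per axis and for area, with its 95% confidence interval. This carries the same test result and also shows size and precision; the choice of interval over p-value is mainly one of reporting style.
3. State that a non-significant result is not evidence of agreement.

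The cost is a few sentences and slightly more analysis, from coordinates and areas already planned; no new visits or data are needed. The limitation is precision: with the half-widths in step 5, agreement would be described, not confirmed.
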